EOT End-of-Treatment FΑ Folinic Acid (Leucovorin) GLP-1 Glucagon-like peptide-1 H&P History & Physical Exam

HRPP Human Research Protections Program

IL1a Interleukin 1-alpha IV (or iv) Intravenously

MTD Maximum Tolerated Dose **LMF** Lipid Mobilizing Factors

LBM Lean Body Mass

NCI National Cancer Institute ORR Overall Response Rate

OS Overall Survival

PAWL Pancreatic Cancer-Associated Weight Loss

[figure not shown]
PBMCs Peripheral Blood Mononuclear Cells

PD Progression of Disease PFS Progression Free Survival

PR Partial Response

PYY Peptide YY

STUDY SCHEMA

Screening Phase

- 1. Informed consent
- 2. Screening
- 3. Eligibility review
- 4. Measure stool fecal elastase
- Measure fatsoluble vitamins

Treatment Phase

Cycle = 28 days

- 1. Measure weight stability
- 2. Assess 24-hour caloric intake
- 3. Assess stool frequency and consistency
- 4. Evaluate microbiome
- 5. Assess activity levels
- 6. Measure quality of life
- 7. Assess inflammatory biomarkers
- 8. Assess the presence of frailty phenotype
- 9. Assess body composition

End-of-Treatment

After C6D28:

- 1. Return pill bottles
- 2. Transition to Soc enzymes

Follow-up Phase

Safety evaluation

Measure fat-soluble vitamins

Survival

Optional sub-study: Followup activity tracking

STUDY SUMMARY

Title	Pancreatic-enzyme replacement therapy with pancreaze (pancrelipase) delayed-release in addition to standard of care for borderline resectable, locally advanced and advanced pancreatic adenocarcinoma patients (PANCAX-3) with cachexia and exocrine pancreatic insufficiency.		
Short Title	PANCAX-3		
Protocol Number	IIT2018-29-[name]-PNCX3		
Phase	Phase 2		
Methodology	Single arm, Single center		
Accrual Duration	18 months		
Study Duration	Approximately 6 months from screening to end of treatment assessment. Subjects will continue to be followed for survival for 36 months.		
Study Center(s)	Single-center, Cedars-Sinai Medical Center		
Objectives	 Feasibility to complete pancreatic enzyme replacement therapy at 8 weeks Measure weight stability at baseline and day 1 of every cycle for 6 months 24-hour caloric intake at baseline, C3D1, and end-of-study Stool frequency at baseline and C3D1 Quality of life assessment baseline and day 1 of every other cycle for 6 months Fitness tracking will be assessed with a wrist-worn wearable activity monitor (e.g., Fitbit Charge HR) continuously from day 1 of cycle 1 until the end of study visit. 		
Number of Subjects	Up to 40 patients (30 evaluable patients)		
Diagnosis and Main Inclusion Criteria	 Age ≥ 18 years of age Biopsy proven pancreatic cancer Borderline resectable, locally advanced or advanced disease Clinical diagnosis of exocrine pancreatic insufficiency Cachexia defined as 5% weight loss in last 6 months 		
Study Product(s), Dose, Route, Regimen	Subjects meeting enrollment criteria will be given Pancrelipase (84,000 lipase units per main meal and 42,000 lipase units per snack). This will be in addition to standard of care procedures including consult with a dietitian and systemic chemotherapy. Subjects will undergo treatment with pancreatic enzymes indefinitely as per standard therapy for patients with EPI.		
Duration of administration	Daily for 24 weeks		
Statistical Methodology	A single institution, phase 2 clinical trial.		

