2.2 Secondary Objectives

- 2.2.1 Measure weight stability at baseline and day 1 of every cycle for 6 months
- **2.2.2** Record 24-hour caloric intake at C1D1, C3D1, and end-of-study
- 2.2.3 Assess stool frequency at C1D1 and C3D1
- 2.2.4 Stool consistency at C1D1 and C3D1
- 2.2.5 Measurement of fat-soluble vitamins at baseline and end-of-study
- **2.2.6** Evaluate microbiome at C1D1 and C3D1
- 2.2.7 Determine if pancreatic enzyme replacement therapy is associated with increased daily activity (steps, counts, stairs, sleep, heart rate, active minutes) using a wristworn fitness tracker (e.g., Fitbit)

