2.4.2 Secondary Hypotheses

Pancreatic enzyme supplementation in addition to standard of care treatment will stabilize weight loss in patients with borderline resectable, locally advanced, and advanced pancreatic cancer patients with exocrine pancreatic insufficiency.

Pancreatic enzyme supplementation, in addition to standard of care chemotherapy and dietitian consultation, will:

- Increase caloric intake
- Make stool frequency more consistent
- Improve stool consistency
- Improve levels of fat-soluble vitamins
- · Alter the microbiome favorably
- Increase daily activity

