3.2 Exclusion Criteria

- **3.2.1** Uncontrolled intercurrent illness including, but not limited to, ongoing or active infection, symptomatic congestive heart failure, unstable angina pectoris, cardiac arrhythmia, or psychiatric illness/social situations that would limit compliance with study requirements.
- 3.2.2 Women who are pregnant or are breastfeeding
- **3.2.3** Dementia or altered mental status that would prohibit the understanding or rendering of informed consent
- **3.2.4** Unable to swallow intact capsules
- **3.2.5** Fibrosing colonopathy: Patients with history of fibrosing colonopathy have been reported to experience advancement to colonic strictures with doses of lipase>6000 units/kg/meal over prolonged periods of time.
- **3.2.6** History of chronic illness associated with malabsorption or nutrient deficiency including but not limited to chronic pancreatitis, cystic fibrosis, celiac disease, Crohn's disease, pernicious anemia and/or prior intestinal resection.
- **3.2.7** Pregnancy, breastfeeding, or of childbearing potential and not willing to use methods of birth control during the study
- **3.2.8** Active drug abuse or intoxication with any substance including alcohol (blood alcohol content >0.08%, legal driving limit)
- **3.2.9** Known allergy to any of the active ingredients in pancreatic enzyme supplementation
- **3.2.10** Concurrent use of pancreatic enzyme supplementation or over the counter supplements which contain lipase, protease, and amylase as active ingredients

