5.0 STUDY PROCEDURES

5.1 List of Study Procedures

5.1.1 Informed Consent – must be obtained within 6 weeks of Day 1

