5.1.20 Activity Monitoring

Wearable activity monitor (e.g., Fitbit Charge HR) activity monitoring to measure step count, heart rate, activity intensity, stairs climbed and sleep. Provide wearable activity monitor with charger and instructions for activity monitoring. Wearable activity monitor will be paired to the subject's personal smartphone. Subject may keep or return the wearable activity monitor at the end-of-study visit. Continued collection of activity monitor data during follow-up will be optional.

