5.2 Screening/Baseline Procedures

Assessments performed exclusively to determine eligibility for this study will be done only after obtaining informed consent. Assessments performed for clinical indications (not exclusively to determine study eligibility) may be used for baseline values even if the studies were done before informed consent was obtained.

All screening procedures used for eligibility verification must be performed within 4 weeks of Day 1 unless otherwise stated. Baseline procedures not required for eligibility verification can occur on Cycle 1, Day 1 of treatment (See section 5.3).

The screening and baseline procedures include:

- Informed consent
- Eligibility review, including:
 - Pregnancy test
- Demographics
- Medical/Surgical history
- Complete physical exam
- Standard of care CT imaging
- Height, weight, vital signs
- Performance status (ECOG or Karnofsky)
- AE (baseline symptom) assessment

- Concomitant medications review
- Labs: CBC/diff, CMP
- Blood draw for fat soluble vitamin levels
- Fecal elastase
 - Note: for maximum flexibility for the patients, the fecal elastase stool sample may be collected during screening or until C1D1 (+ 7 days).
 Patients will be encouraged to provide the fecal elastase stool sample prior to starting treatment, if possible.

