5.7 Removal of Subjects from Study

Patients can be taken off the study treatment and/or study at any time at their own request, or they may be withdrawn at the discretion of the investigator for safety, behavioral or administrative reasons. The reason(s) for discontinuation will be documented and may include:

³ASA-24 is completed electronically and may be completed within 7 days of the visit.

⁴Subjects will complete a daily compliance diary for the first two cycles only. Diary will be given to patients on Day 1 of the first two cycles. Subjects will return diary to study staff for compliance calculation on completion of each of the first two cycles.

⁵Fat-soluble vitamin labs to be drawn include: Vitamin A: serum retinol; Vitamin D:25-Hydroxy; Vitamin E: serum alpha-tocopherol; Vitamin K: PIVKA-II and prothrombin time.

⁶The patients will be followed on treatment for the 24-week study treatment period. Treatment may continue beyond the study treatment period, at the physician's discretion, per standard of care. Pancreaze will be dispensed at C1D1 and C4D1, and subjects will return remaining supply at C4D1 and the end-of-treatment visit for drug accountability by Research Pharmacy.

⁷Stool sample may be collected during screening or until C1D1 + 7 days.

⁸ Window for C3D1 sample is +/- 7 days.

⁹Subjects will continue to take the study drug until the Cycle 6 Day 28 time point. Subjects should be reminded to discontinue study supply of Pancreaze following Cycle 6 Day 28.

- **5.7.1** Patient voluntarily withdraws (follow-up permitted);
- **5.7.2** Patient withdraws consent (termination of treatment and follow-up);
- **5.7.3** Patient is unable to comply with protocol requirements;
- **5.7.4** Patient experiences toxicity that makes continuation in the protocol unsafe;
- **5.7.5** Treating physician judges continuation on the study would not be in the patient's best interest;
- **5.7.6** Patient becomes pregnant (pregnancy to be reported along same timelines as a serious adverse event);
- 5.7.7 Lost to follow-up. If a research subject cannot be located to document survival after a period of 2 years, the subject may be considered "lost to follow-up." All reasonable efforts must be made to locate subjects to determine and report their ongoing status. Lost to follow-up is defined by the inability to reach the subject after a minimum of three documented phone calls, faxes, or emails as well as lack of response by subject to one registered mail letter.

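### No wearable recording is scheduled before the first dose, so this single-arm trial cannot estimate a device-measured change in activity from before therapy (objective 2.2.7)

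*Combined protocol and SAP*

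**What the plan says.** Objective 2.2.7 is to "Determine if pancreatic enzyme replacement therapy is associated with increased daily activity", measured with a wrist-worn tracker. The list of expected effects in section 2.4.2 includes "Increase daily activity". The Study Summary describes a single-arm design and has tracking run "continuously from day 1 of cycle 1 until the end of study visit".

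On drug supply, footnote 6 to the Time and Events Table (section 5.6) states: "Pancreaze will be dispensed at C1D1 and C4D1".

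On the device, section 5.1.20 says "Provide wearable activity monitor with charger and instructions for activity monitoring" but gives no date of issue. Section 5.3.1 places the device function check on Day 1 of each cycle, so the first check is on C1D1. The screening and baseline list in section 5.2 contains no device item; that section adds that "Baseline procedures not required for eligibility verification can occur on Cycle 1, Day 1 of treatment".

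Two passages point less clearly. The activity endpoint in section 2.5.2 is collected every day for as long as the study lasts, and the Study Duration row of the Study Summary counts from screening.

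Section 9.2 plans regression of the secondary endpoints on baseline variables, with random effects for repeated measures. It defines no baseline for activity.

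**The concern.** With no control arm, each patient's own level before treatment is the natural comparator for a claim that activity increased. The device starts recording on the day the drug starts, so it does not capture that level. A rising or falling curve on treatment cannot show whether patients are above or below where they were before therapy. Section 1.4 says the activity data may support the efficacy of the intervention, so they are meant to be more than descriptive.

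**Working it through.** The plan gives no figure to reproduce here. The check compares dates in the schedule and then looks at what contrasts remain.

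**1. Scheduled device days per patient (nominal)**
- Before the first dose: tracking starts C1D1 (Study Summary) and drug starts C1D1 (5.6, footnote 6), so 0 full days. At most there are some hours of a clinic-visit day before the first capsule.
- On treatment: 6 cycles x 28 days = 168 days.
- After the last dose, up to the End-of-Study visit (5.4): 30 days, or 30 - 7 = 23 to 30 + 7 = 37 with the visit window. Section 5.1.20 makes tracking beyond that visit optional.

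**2. Early cycle 1 as a stand-in baseline**

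If the baseline window already contains a fraction f of the effect, the estimated change is (1 - f) times the true change. As an illustration only, assume the effect rises linearly to its full size over R days and then stays level. With days 1 to 7 as baseline and R of at least 7, f = (1 + 2 + ... + 7)/(7R) = 4/R. With day 1 alone, f = 1/R.

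| Assumed R (days) | Share kept, days 1-7 | Share kept, day 1 only |
|---|---|---|
| 7 | 1 - 4/7 = 43% | 1 - 1/7 = 86% |
| 14 | 1 - 4/14 = 71% | 1 - 1/14 = 93% |
| 28 | 1 - 4/28 = 86% | 1 - 1/28 = 96% |

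R is an assumption, because the documents give no onset time. The day-1 column looks better but rests on a single clinic-visit day.

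**3. Activity against enzyme intake**

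The daily log covers the first two cycles only (5.6, footnote 4): 2 x 28 = 56 of 168 days, or 33%. Dose changes are dated (4.1.3), and returned supply is counted at C4D1 and at end of treatment (5.6, footnote 6), which gives coarse exposure data for the rest. Any such relation is confounded, since sicker patients may both eat and move less.

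**4. On drug against after drug**

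The end-of-treatment visit falls 0 to 7 days after the last dose (5.3.3), and patients may move to standard-of-care enzymes there.
- A patient who moves has 0 to 7 days off enzymes. The largest share of the after-drug period is 7/23 = 30%. Days on standard-of-care enzymes run from 23 - 7 = 16 to 37 - 0 = 37.
- A patient who does not move has 23 to 37 days off.

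Section 4.1.1 expects enzyme treatment to continue indefinitely, so this period is not a clean off-therapy reference.

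**5. Room for a run-in**

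Section 5.2 sets screening within 4 weeks of Day 1: 4 x 7 = 28 days at most. Consent "must be obtained within 6 weeks of Day 1", which is earlier, but a run-in kept inside the screening window is limited to 28 days. No minimum interval between consent and Day 1 is stated, so some run-ins would be short.

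**The case against.** The strongest reply is that the endpoint wording in 2.5.2, read with the Study Duration row, could include screening. That is a real ambiguity and should be reconciled. It does not supply a baseline, however: the Study Summary's start date is the more specific statement, and nothing in 5.1.20 or 5.2 issues a device earlier. The wearable row of the table in 5.6 is broken in the available text, so I rely on it for neither side.

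A second reply is that 2.2.7 asks only about association and never defines the contrast as before against after. That is fair. A reader might infer that the objective cannot be addressed at all or that the wearable data are of no use. The documents do not support that: the repeated-measures model in 9.2 gives an on-treatment trend, early cycle 1 gives an approximate baseline, and the correlations planned in section 1.4 need no pre-dose data.

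A third reply is that a run-in would still leave a before-after change confounded by chemotherapy, dietitian input and the course of disease. This stands. A run-in gives a starting level, not a causal effect.

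The frailty assessment includes an activity questionnaire (Appendix E), but it is self-reported and does not give a device baseline.

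**Conclusion.** The point holds for the wearable measure. The plan schedules no full device day before the first dose, so a device-measured change from before therapy cannot be estimated for 2.2.7 and the matching hypothesis in 2.4.2. This rests on taking the explicit C1D1 start in the Study Summary as governing.

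The size is limited. It affects one of seven secondary objectives, and the primary endpoint is untouched. What remains is an on-treatment trend, attenuated to an unknown degree if read as change from baseline and the effect starts early, plus confounded exposure and after-drug contrasts. The percentages in the table depend entirely on the assumed onset.

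A reader might extend the criticism to the other secondary measures taken around C1D1. The documents give no basis for sizing such a problem, and it is not part of this point. I would class the change as a cheap improvement.

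**What to change.** - **Study Summary, 5.1.20, 5.2 and 5.6:** issue the same device after consent, within the existing screening window (at most 28 days) and without delaying treatment. Align the collection period in 2.5.2 with this.
- **Section 9.2:** define baseline activity as the mean over valid-wear days before the first dose, with the minimum number of days set by the sponsor. Analyse change from that baseline in the planned repeated-measures model. Report patients without a valid run-in separately, as on-treatment trend only.
- **Enzyme use in the run-in:** criterion 3.2.10 excludes "Concurrent use of pancreatic enzyme supplementation or over the counter supplements" with certain active ingredients, but it states no washout. Use the concomitant-medication review already done at screening to note any such use. Section 4.2 limits what must be entered in the database, so the note needs an explicit place.
- **Fallback:** if a run-in is impracticable, or for patients already enrolled, reword 2.2.7 and the matching item in 2.4.2 as an on-treatment trend. This costs only text.

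The cost is wording in the sections named and a few devices given to patients who then fail screening. Some run-ins will be short or absent, and the confounding by chemotherapy and dietitian input remains.

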1.0 BACKGROUND AND RATIONALE

1.1 Disease Background

Pancreatic-enzyme replacement therapy (PERT) is the standard of care to prevent maldigestion, malnutrition, and excessive weight loss in patients with exocrine pancreatic insufficiency (EPI) due to chronic pancreatitis (CP) or pancreatic surgery (PS). The utility of this therapy for patients with EPI in the setting of pancreatic cancer is unclear.

Pancreatic cancer is the fourth leading cause of cancer related deaths in the United States and associated with poor prognosis. EPI is a common complication of pancreatic cancer. There are several mechanisms for this, which includes tumor induced pancreatic duct obstruction, pancreatic fibrosis and atrophy. Under normal circumstances, digestive enzymes secreted from the pancreas are essential for digestion of proteins and fats. Impairment in enzyme secretion can lead to malabsorption of these compounds producing symptoms of delayed gastric emptying, increased bloating, abdominal fullness/discomfort, nausea, and early satiety in addition to potential nutrient deficiencies. Studies have shown a prevalence varying from 50-89% demonstrated by low fecal elastase [1-3]. Studies have shown that cachexia worsens the prognosis of patients with pancreatic cancer [4, 5]. Weight loss has also been associated with a poorer quality of life in patients with pancreatic cancer and those with stabilization of weight reported a greater global quality of life score[5]. Studies have shown small peak or no peak in the release of pancreatic enzymes in patients with pancreatic cancer[6]. DiMagno showed lower trypsin, lipase and bicarbonate secretion in patients with non-resectable pancreatic cancer and pancreatic duct obstruction [7]

Pancreatic enzyme supplementation has demonstrated benefit for patients with EPI due to chronic pancreatitis. Two previous randomized-controlled trials have evaluated the impact of enzyme supplementation among patients with chronic pancreatitis. Both studies demonstrated improvement in measures of fat absorption (coefficient of fat absorption, fecal fat excretion) among patients treated with enzyme supplements [8, 9]. In addition, the study reported by Safdi et al also noted that the enzyme treatment group experienced reduced stool frequency, improved stool consistency and greater physician-assessed global symptom improvement [10]. No serious adverse events related to study medication occurred in either trial.

However, the evidence for the use of pancreatic enzymes in pancreatic cancer is limited. Despite this, according to the guidelines published in Gut in 2005 for the management of patients with pancreatic cancer, pancreatic enzymes supplementation should be used to maintain weight and increase quality of life [11]. A double blinded randomized controlled trial looking at 21 patients with unresectable cancer in the head of the pancreas with obstructive jaundice and suspected pancreatic duct obstruction were randomized to placebo or enteric coated pancreatin enzyme supplementation. Patients were given 25000 units of lipase with snacks and 50,000 units with meals. The investigators found that patients on the enzyme supplementation gained 1.2% body weight compared to placebo who lost 3.7% body weight over 4-week follow-up. Fat absorption coefficient improved by 12% in those receiving enzymes [12]. Dominguez Munoz et al presented an abstract at the APA in 2013 of a retrospective non-randomized case series of 76 patients with nonresectable pancreatic cancer who were receiving Creon replacement with nutritional counseling and palliative care or standard palliative care without enzyme therapy. They found that the median survival of patients who were receiving pancreatic enzyme therapy was longer than those with standard palliative care (301 days versus 89 days). This study was limited by the lack of measurement of EPI [13].

Our objective is to assess weight stability, functional changes, and quality of life when pancreaze (pancrelipase) delayed-release 84,000-lipase unit capsules, for main meals, and 42,000-lipase unit capsules, for snacks, are added to standard of care in patients with EPI due to pancreatic adenocarcinoma. This will be the first prospective study of this particular formulation in addition to standard of care in advanced pancreatic cancer patients. We will treat 30 consecutive patients with borderline resectable, locally advanced and advanced pancreatic cancer who present with weight loss and exocrine pancreatic insufficiency with this advanced formulation of pancreaze.

Standard of Care Nutrition Screening and Clinical Assessment:

A full nutrition assessment involves the following elements: obtaining a food history, evaluation of anthropometric measurements, review of medical history, biochemical data, medical tests and procedures, and completion of a nutrition-focused physical assessment [14]. Routine assessment of food intake should include patient estimate of overall food intake and 24-h food recall [15]. An oncology focused assessment also involves reviewing the oncologic treatment plan with the goal to determine current and anticipated nutrition issues [16-18]. This information is all assimilated and used to formulate a plan to address existing and potential influences on malnutrition. Dietitians play a central role in the successful management of pancreatic cancer-associated weight loss (PAWL). Nutrition interventions for PAWL have improved weight [19], quality of life, and outcomes [14, 20, 21]. Dietitians can provide essential dietary suggestions, identify pancreatic exocrine insufficiency, and provide recommendations for oral nutritional supplementation and specialized nutrition support [22]. Dietitians may also provide more detailed advice on diet and pancreatic enzyme supplementation for management of symptoms of EPI [23-26].

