2.5 Endpoints

2.5.1 Primary endpoint

 Measure patient compliance to take pancreatic enzyme replacement therapy using a patient reported Pancreaze daily accountability log. Patient compliance will be defined as patients taking ≥ 50 % of the needed total lipase units. The primary endpoint will be met if at least 50% of the subjects in each cohort take at least 50% of the total needed lipase units within the first 8 weeks of treatment.

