9.0 STATISTICAL CONSIDERATIONS

9.1 Power Assessment

The primary hypothesis to be tested is whether the percentage of patients who complete the course of pancreatic enzyme replacement therapy at 8 weeks is at least 50% for each of the three cancer stage subgroups: borderline resectable, locally advanced and advanced pancreatic cancer. We assumed a sample size equal to 10 patients for each group. The minimum detectable difference from the proportion 0.5 is 0.417 using a Binomial Exact test with Bonferroni correction. Thus, we will declare the sustainability of the therapy if 9 or more patients complete the treatment for each subgroup.

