9.2 Data Analysis Plan

The primary hypothesis to be tested is whether is the percentage of patients who complete the pancreatic enzyme replacement therapy at 8 weeks is at least 50% for each of the three cancer stage subgroups: borderline resectable, locally advanced and advanced pancreatic cancer. A 95% confidence interval [1] for the proportion of treatment completeness will be calculated for each cancer stage. The statistical analysis will be performed in three steps for all secondary endpoints: 1) Descriptive analysis: Measures of central tendency (mean, median and mode), measures of variability (standard deviation, range and quantiles). Standard distribution plots such as profiles-plots for repeated measures and box-plots will be constructed to examine the distribution of the data. 2) Univariable Analysis and 3) Multivariable analysis: The linear regression model will be applied to explain the secondary endpoints as a function of the patient's baseline variables. Assumptions of the linear regression model will be examined. If the assumptions are not met. Generalized Additive models for Location, Scale and Shape (GAMLSS) which provide a general framework for extending a standard linear model will be applied [2]. The goodness of fit for each model will be accessed through a residual analysis using Worm-plots [51] and variable selection will be performed as outlined by Harrell [4]. Random effects will be added to describe the repeated measures. In addition, overall survival curve will be estimated using the Kaplan-Meier method with 95% confidence interval. All tests of hypotheses will be two-sided and a significance level of 0.05 and calculations will be performed using R, version 3.2.3 [5].

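### The primary decision rule is a fixed count of 9 that fits only a cohort of 10, and nothing in the plan secures 10 patients per stage cohort

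*Combined protocol and SAP*

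**What the plan says.** Section 9.1 sizes the trial by stage: "We assumed a sample size equal to 10 patients for each group". It continues: "The minimum detectable difference from the proportion 0.5 is 0.417 using a Binomial Exact test with Bonferroni correction". From this it derives the decision rule, which is to "declare the sustainability of the therapy if 9 or more patients complete the treatment for each subgroup". The rule is a count with no denominator.

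Section 2.5.1 also judges the endpoint cohort by cohort, but as a proportion: "at least 50% of the subjects in each cohort take at least 50% of the total needed lipase units". Section 9.2 adds a 95% confidence interval per stage and says "All tests of hypotheses will be two-sided and a significance level of 0.05".

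On accrual:
- Section 1.1 states: "We will treat 30 consecutive patients with borderline resectable, locally advanced and advanced pancreatic cancer".
- Section 10.3 numbers subjects in order of consent and describes no stage slot, cap or cohort closure.
- Section 4.5 replaces withdrawals without saying that the replacement must be of the same stage.
- The Study Summary allows up to 40 patients, 30 of them evaluable. Appendix I explains the 40 as room to replace patients who could not be evaluated.
- Appendix I also records that the total fell from 45 to 30 as the subgroup size fell from 15 to 10.

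**The concern.** A cut-off of 9 has the intended error rate and power only when the cohort holds exactly 10 evaluable patients. In a smaller cohort it is very hard or impossible to reach; in a larger one it is too lenient. Success is required in every cohort, so one short cohort is enough to block the primary conclusion whatever the compliance. The plan neither fixes the cohort sizes nor says what cut-off applies when a cohort is not 10.

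**Working it through.** **Inputs.** From 9.1: n = 10 per cohort, null proportion 0.50, detectable difference 0.417 (alternative 0.917), exact binomial test, Bonferroni correction over three cohorts (0.05/3 = 0.0167), cut-off 9. From 1.1 and the Study Summary: 30 patients, ceiling 40. Two things are not in the documents. Power is taken as 80%, and the stage mix is varied.

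**1. The plan's own figure.** At n = 10:
- Error: P(X ≥ 9 | 0.5) = (10 + 1)/1024 = 0.0107, below 0.0167.
- Power: P(X ≥ 9 | 0.917) = 10 × 0.917⁹ × 0.083 + 0.917¹⁰ = 0.801.
- Solving for 80% power gives a difference of 0.4167, which matches 0.417.

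So 9.1 reproduces at n = 10, one-sided. Two-sided, 9 of 10 has p = 2 × 0.0107 = 0.0215, above 0.0167.

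**2. How often uncapped accrual gives usable cohorts.** With N consecutive patients and stage shares p₁, p₂, p₃, the cohort sizes are multinomial. For N = 30, P(10/10/10) = 30!/(10!)³ × (p₁p₂p₃)¹⁰. This is largest at equal shares, so 2.7% is an upper bound for any mix.

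| Assumed mix | P(10/10/10), N=30 | P(some cohort < 9), N=30 | P(some cohort < 9), N=40 all analysed |
|---|---|---|---|
| equal | 2.7% | 76% | 14% |
| 25/35/40 | 1.5% | 86% | 33% |
| 20/30/50 | 0.3% | 96% | 66% |

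**3. What a count of 9 does in a single cohort of another size.** Error is P(X ≥ 9 | n, 0.5):
- n = 8 or fewer: 9 cannot be reached.
- n = 9: error 0.002; power 0.917⁹ = 0.458, down from 0.801.
- n = 11: 67/2048 = 0.033.
- n = 12: 299/4096 = 0.073.

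The Bonferroni level of 0.0167 is exceeded from n = 11.

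**4. How far the leniency can reach the joint conclusion.** If all three cohorts hold at least 9 of 30 patients, the largest holds at most 30 − 9 − 9 = 12. A false joint declaration therefore cannot exceed 7.3% with 30 patients.

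**5. Exact cut-offs by cohort size** (smallest r with P(X ≥ r | n, 0.5) at or below the level):

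| n | one-sided 0.0167 | two-sided 0.0167 (0.0083 per tail) |
|---|---|---|
| 8 | 8 | 8 |
| 9 | 9 | 9 |
| 10 | 9 | 10 |
| 11 | 10 | 10 |
| 12 | 11 | 11 |
| 13 | 11 | 12 |

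**The case against.** The strongest reply is that 10 per cohort is a design target. The word consecutive appears only in the background narrative, the amendment log moves the total and the subgroup size together, and 30 is 3 × 10. If each cohort is filled to 10 and then closed, the probabilities in step 2 do not apply. This is a fair reading of intent and it stands as such. No operative section carries it out, however, and even capped cohorts can end short.

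A second reply is that other text works at any size. The proportion in 2.5.1 is met by 8 of 8, 9.2 gives an interval for whatever n is reached, and 9.1 names the test from which a new cut-off could be calculated. That is true, but 9.1 does not tell the analyst to recalculate. Read literally, its count fails a cohort of 8 in which everyone complied.

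A reader might also infer that the trial risks a badly inflated false-positive primary result, because a count of 9 has error 13.3% at n=13 and 21.2% at n=14. The documents do not support this for 30 patients: a cohort of 13 leaves 17 for the other two, so one of them has at most 8 and the joint declaration is impossible. Those sizes matter only for claims about a single cohort or if more than 30 patients are analysed.

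The ceiling of 40 does not settle the matter. Its stated purpose is replacement. If all 40 places were filled and analysed, a short cohort would be less likely, but at least one cohort would hold 14 or more (40/3 > 13).

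**Conclusion.** The point holds as a defect in the primary decision rule: its count is calibrated at n=10 only, and the plan neither secures that size nor gives a cut-off for any other. Within 30 patients the more likely harm is a cohort that cannot pass; the leniency is real but limited to 3.3% at n=11 and 7.3% at n=12.

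The 76% to 96% chance of a cohort below 9 is conditional on consecutive, uncapped accrual. All mixes are assumptions, since the documents give none; only the 2.7% bound is free of the mix. It would go too far to conclude that the trial will almost never reach 10 per cohort, because the amendment log points to an intention to fill each one.

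**What to change.** **In 9.1**, replace the fixed 9 by the exact binomial critical value for the evaluable cohort size obtained, and state the sidedness before the data are examined. One-sided 0.0167 keeps the plan's 9 of 10. The two-sided testing stated in 9.2 would require 10 of 10, with power at 0.917 of 0.917¹⁰ = 42% instead of 80%. Sections 9.1 and 9.2 should be brought into line on this. The table costs nothing. It restores the error rate but not the power of small cohorts: at 0.917, 8 of 8 has power 50% and 9 of 9 has 46%.

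**In 10.3 and 4.5**, if 10 per cohort is the intent, say so: record stage at registration, cap each cohort at 10 evaluable patients and replace within the same stage. Amend the sentence in 1.1 to match. The cost is slower accrual in the least common stage. For an 80% chance of filling all three cohorts, about 42 eligible patients must present at equal shares, 49 at 25/35/40 and 62 at 20/30/50. Patients who arrive after their cohort has closed would not be enrolled, but the search could outlast the planned 18 months. If they are enrolled, the total passes the ceiling of 40. A cohort may therefore still end short, so the size-dependent cut-off is needed in either case.
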